6.2.3. Analysis of Safety

SAEs considered related to vaccination, related to lack of vaccine efficacy, related to study procedures, or leading to withdrawal of the subject from the study will be tabulated for Years 1, 3, and 5.

The analysis will be performed overall, by country, and by the number of doses of Prevenar 13 received before the study (2 or 3 doses).

7. STATISTICAL CALCULATIONS

7.1. Derived and Transformed Data

- The SAS code for calculating age in years will be `INT(INTCK("MONTH", birth date, vaccination date)/12)`.
- Duration from the last primary vaccination to any persistence time point will use the day of primary vaccination as Day 0.
- Activity date is defined as the date associated with any activity performed at the indicated visit.
- If a percentage calculation has no eligible subjects, then the sample size will be “0” and the percent value will be “.”.

7.1.1. Immunogenicity

- The cutoff value is defined by the laboratory before the analysis and is described in [Section 5.7.3](#) of the protocol.
- The GMT/GMC calculations are performed by taking the antilog of the mean of the log titer/concentration transformations. Antibody titers/concentrations below the cutoff of the assay will be given an arbitrary value of half the cutoff for the purpose of GMT/GMC calculation.
- Handling of missing data: for a given subject and a given immunogenicity measurement, missing or nonevaluable measurements will not be replaced.

7.1.2. Safety and Reactogenicity

- For a given subject and the analysis of solicited events within 4 days after vaccination, missing or nonevaluable measurements will not be replaced. Therefore, the analysis of the solicited events based on the total vaccinated cohort will include only vaccinated subjects for doses with documented safety data (ie, event screen completed). More specifically, the following rules will be used:
 - Subjects who documented the absence of a solicited event after 1 dose will be considered not having that event after that dose.

- Subjects who documented the presence of a solicited event and fully or partially recorded daily measurements over the solicited period will be included in the summaries at that dose and classified according to their maximum observed daily recording over the solicited period.
- Subjects who documented the presence of a solicited event after 1 dose without having recorded any daily measurements will be assigned to the lowest intensity category at that dose (ie, 37.5°C for fever or Grade 1 for other events).
- Doses without symptom sheets documented will be excluded.
- For analysis of unsolicited AEs, such as SAEs or AEs by primary MedDRA term, and for the analysis of concomitant medications, all vaccinated subjects will be considered. Subjects who did not report the event or the concomitant medication will be considered as subjects without the event or the concomitant medication.
- For the analysis, rectal temperatures will be coded as follows:

Grade	Temperature
0	<38.0°C
1	≥38.0°C - ≤39.0°C
2	>39.0°C - ≤40.0°C
3	>40.0°C

When temperature is measured by the oral, axillary, or tympanic route, the corresponding rectal temperature will be derived by adding 0.5°C to the temperature recorded. The above intensity grade will be applied to the derived rectal temperature.

- The way the percentage of subjects will be derived will depend on the event analyzed (see table below for details). As a result, the N value will differ from one table to another.

Analysis	N used for deriving % per subject for vaccination phase
Concomitant vaccination	All subjects with study vaccine administered
Solicited general event	All subjects with at least 1 solicited general event documented as either present or absent (ie, event screen completed)
Solicited local event	All subjects with at least 1 solicited local event documented as either present or absent (ie, event screen completed)
Unsolicited adverse event	All subjects with study vaccine administered
Concomitant medication	All subjects with study vaccine administered

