**Table 15. Solicited General Adverse Events**

Drowsiness
Fever
Irritability/Fussiness
Loss of appetite

Fever is defined as rectal temperature  $\geq 38^{\circ}\text{C}$ /axillary temperature  $\geq 37.5^{\circ}\text{C}$ /oral temperature  $\geq 37.5^{\circ}\text{C}$ /tympanic temperature on oral setting  $\geq 37.5^{\circ}\text{C}$ /tympanic temperature on rectal setting  $\geq 38^{\circ}\text{C}$ .

Note: Temperature will be recorded in the evening. Should additional temperature measurements be performed at other times of day, the highest temperature will be recorded in the eCRF.

**8.1.4. Clinical Laboratory Parameters and Other Abnormal Assessments Qualifying as Adverse Events or Serious Adverse Events**

In absence of diagnosis, abnormal laboratory findings (e.g. clinical chemistry, haematology, urinalysis) or other abnormal assessments (e.g. medical imaging) that are judged by the investigator to be clinically significant will be recorded as AE or SAE if they meet the definition of an AE or SAE (refer to [Section 8.1.1](#) and [Section 8.1.2](#)). Clinically significant abnormal laboratory findings or other abnormal assessments that are present at baseline and significantly worsen following the start of the study will also be reported as AEs or SAEs. However, clinically significant abnormal laboratory findings or other abnormal assessments that are associated with the disease being studied, unless judged by the investigator as more severe than expected for the subject's condition, or that are present or detected at the start of the study and do not worsen, will not be reported as AEs or SAEs.

The investigator will exercise his or her medical and scientific judgement in deciding whether an abnormal laboratory finding or other abnormal assessment is clinically significant.

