**Table 19. Intensity Scales for Solicited Symptoms in Infants/Toddlers**

Adverse Event	Intensity grade	Parameter
Irritability/Fussiness	0	Behaviour as usual
	1	Mild: Crying more than usual/no effect on normal activity
	2	Moderate: Crying more than usual/interferes with normal activity
	3	Severe: Crying that cannot be comforted/prevents normal activity
Drowsiness	0	Behaviour as usual
	1	Mild: Drowsiness easily tolerated
	2	Moderate: Drowsiness that interferes with normal activity
	3	Severe: Drowsiness that prevents normal activity
Loss of appetite	0	Appetite as usual
	1	Mild: Eating less than usual/no effect on normal activity
	2	Moderate: Eating less than usual/interferes with normal activity
	3	Severe: Not eating at all

\*Fever is defined as rectal temperature  $\geq 38^{\circ}\text{C}$ /axillary temperature  $\geq 37.5^{\circ}\text{C}$ /oral temperature  $\geq 37.5^{\circ}\text{C}$ /tympanic temperature on oral setting  $\geq 37.5^{\circ}\text{C}$ /tympanic temperature on rectal setting  $\geq 38^{\circ}\text{C}$ .

The maximum intensity of local injection site redness/swelling will be scored as follows:

0	:	None
1	:	> 0 - $\leq$ 10 mm
2	:	> 10 - $\leq$ 30 mm
3	:	> 30 mm

The maximum intensity of fever will be scored as follows:

	Oral/Axillary/Tympanic temperature on oral setting	Rectal/Tympanic temperature on rectal setting
0 :	< 37.5°C	< 38.0°C
1 :	$\geq 37.5^{\circ}\text{C}$ - $\leq 38.5^{\circ}\text{C}$	$\geq 38.0^{\circ}\text{C}$ - $\leq 39.0^{\circ}\text{C}$
2 :	> 38.5°C - $\leq 39.5^{\circ}\text{C}$	> 39.0°C - $\leq 40.0^{\circ}\text{C}$
3 :	> 39.5°C	> 40.0°C

The investigator will assess the maximum intensity that occurred over the duration of the event for all unsolicited AEs (including SAEs) recorded during the study. The assessment will be based on the investigator's clinical judgement.

The intensity should be assigned to one of the following categories:

- 1 (mild) = An AE which is easily tolerated by the subject, causing minimal discomfort and not interfering with everyday activities.
- 2 (moderate) = An AE which is sufficiently discomforting to interfere with normal everyday activities.
- 3 (severe) = An AE which prevents normal, everyday activities (in a young child, such an AE would, for example, prevent attendance at school/kindergarten/a day-care centre and would cause the parent(s)/LAR(s) to seek medical advice.)

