6.1.3. Analysis Of Safety

The primary analysis will be performed on the total vaccinated cohort. If, for any vaccine group, more than 5% of the enrolled subjects are eliminated from the ATP cohort for safety, then a second analysis will be performed on the ATP cohort for safety to support the analyses of the total vaccinated cohort.

All percentages/proportions described below will be tabulated with exact 95% CIs.

Timing between reconstitution of and vaccination with MenACWY-TT will be summarized per vaccine group and overall.

The percentages of subjects with at least 1 local event (solicited and unsolicited), with at least 1 general event (solicited and unsolicited), and with any event or AE during the 4-day solicited follow-up period will be tabulated. The same calculations will be performed for events rated as Grade 3 and for events related to vaccination.

The percentage of subjects reporting each individual solicited local (any grade, Grade 3, and requiring medical advice) and general (any grade, Grade 3, related, Grade 3 and related, and requiring medical advice) event during the 4-day follow-up period (Day 0 – Day 3) after vaccination will be tabulated. Occurrence of fever will also be reported per 0.5°C cumulative increments up to >40.0°C. All of the above calculations will also be performed by country and by the number of doses of Prevenar 13 received before the study (2 or 3 doses).

The percentages of subjects using concomitant medication (any medication, any antipyretic, any antipyretic taken prophylactically, respectively) during the 4-day and 31-day follow-up periods (Day 0 – Day 3 and Day 0 – Day 30, respectively) after each vaccination will be summarized.

The verbatim reports of unsolicited AEs will be reviewed by the medical monitor and the signs and symptoms will be coded according to MedDRA terminology.

The percentages of subjects with unsolicited AEs within 31 days after vaccination (Day 0 – Day 30) will be tabulated by vaccine group and by MedDRA preferred term. Similar tabulations will also be performed by country and by the number of doses of Prevenar 13 received before the study (2 or 3 doses). Likewise, tabulations by vaccine group and MedDRA preferred term will also be done for Grade 3 unsolicited AEs, for unsolicited AEs possibly related to vaccination, and for Grade 3 unsolicited AEs possibly related to vaccination.

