7.2. Sensitivity Analyses

- In case the number of subjects who documented the presence of a solicited event after 1 dose without having recorded any daily measurement exceeds 1%, a sensitivity analysis will be carried out to assess the impact of assigning the lowest intensity for the event. Two (2) additional analyses will be performed for solicited events collected during the 4-day (Day 0 – Day 3) follow-up period:
 - In the first sensitivity analysis, subjects who documented the presence of an event without having recorded any daily measurement will be assigned to the highest intensity category (ie >39.5°C for fever or Grade 3 for other events), while the subjects without documentation will be excluded.
 - In the second sensitivity analysis, both subjects who documented the presence of an event without having recorded any daily measurement and subjects without documentation will be excluded.

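### SAP 7.1.2 adds 0.5°C to every tympanic reading, so readings taken on rectal setting can be graded one level higher than the protocol grades them; two fever values in the SAP are also on the oral scale

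*SAP*

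**What the plan says.** **SAP.** Section 7.1.2 prints one fever scale, in rectal terms: Grade 0 below 38.0°C, Grade 1 from 38.0 to 39.0°C, Grade 2 above 39.0 to 40.0°C, Grade 3 above 40.0°C. For other routes it states: "When temperature is measured by the oral, axillary, or tympanic route, the corresponding rectal temperature will be derived by adding 0.5°C". The rectal grades are then applied to the derived value. The device setting is not mentioned.

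**Protocol.** Table 19 has two fever columns. One is headed "Oral/Axillary/Tympanic temperature on oral setting" and starts fever at 37.5°C. The other is headed "Rectal/Tympanic temperature on rectal setting" and starts fever at 38.0°C. The definition under Table 15 makes the same split and lists "tympanic temperature on rectal setting" with its own 38°C threshold. Protocol 5.6.9 and 6.7.1 repeat it.

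**Missing intensities.** When a fever is reported with no daily measurement, SAP 7.1.2 assigns "the lowest intensity category at that dose (ie, 37.5°C for fever or Grade 1 for other events"). Protocol 10.5 has the same 37.5°C. In the first sensitivity analysis of SAP 7.2 these subjects are "assigned to the highest intensity category (ie >39.5°C for fever or Grade 3 for other events").

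**Output.** SAP 6.1.3 tabulates solicited fever by grade and adds: "Occurrence of fever will also be reported per 0.5°C cumulative increments up to >40.0°C".

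**The concern.** A tympanic thermometer on rectal setting already displays a value on the rectal scale, and the protocol grades it that way. Adding 0.5°C shifts it a second time. The error can only go upward, so fever incidence and Grade 3 fever could be overstated.

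Solicited symptoms are a secondary endpoint, tabulated by vaccine group and also by country and number of previous Prevenar 13 doses, so a few misgraded readings could show in a small subgroup. SAP 9 names six changes from the planned analyses, and none concerns fever grading or temperature conversion.

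The 37.5°C and >39.5°C labels raise a smaller question of the same kind. They are the bottom of Grade 1 and the bottom of Grade 3 on the protocol's oral column, but they sit beside a table that has only rectal limits.

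**Working it through.** **Inputs** (Protocol Table 19; SAP 7.1.2), in °C:

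| Grade | Protocol: oral, axillary, tympanic on oral setting | Protocol: rectal, tympanic on rectal setting | SAP scale (rectal) |
|---|---|---|---|
| 0 | <37.5 | <38.0 | <38.0 |
| 1 | 37.5 to 38.5 | 38.0 to 39.0 | 38.0 to 39.0 |
| 2 | >38.5 to 39.5 | >39.0 to 40.0 | >39.0 to 40.0 |
| 3 | >39.5 | >40.0 | >40.0 |

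**Step 1. Reproduce the protocol's oral column from the SAP rule.** For a non-rectal reading *t*, the SAP grade is the rectal grade of *t* + 0.5. Subtracting 0.5 from the rectal limits 38.0, 39.0 and 40.0 gives 37.5, 38.5 and 39.5, which are the protocol's oral limits. At every 0.1°C step from 34.0 to 43.0°C (91 values), the two grades differ at none. The offset is right for oral, axillary and oral-setting tympanic readings.

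**Step 2. Apply the same rule to a tympanic reading on rectal setting.** The protocol limits are 38.0, 39.0 and 40.0 on the reading as recorded. The SAP's effective limits are 37.5, 38.5 and 39.5. The grades differ between each pair of limits:

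| Reading (°C) | SAP derived value | Protocol grade | SAP grade |
|---|---|---|---|
| 37.5 to 37.9 | 38.0 to 38.4 | 0 | 1 |
| 38.6 to 39.0 | 39.1 to 39.5 | 1 | 2 |
| 39.6 to 40.0 | 40.1 to 40.5 | 2 | 3 |

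That is 5 + 5 + 5 = 15 values at 0.1°C resolution, each one grade too high. All other values agree.

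**Step 3. Try the opposite blanket rule.** If no tympanic reading received the offset, oral-setting readings in the same three bands would be one grade too low. Neither blanket rule matches the protocol; the rule has to follow the setting. With the offset limited to oral, axillary and oral-setting tympanic readings, no grade differs.

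**Step 4. The two labels.**

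- Category assigned directly: Grade 1 in the main analysis and Grade 3 in the first sensitivity analysis. Both are as intended.
- Number inserted as a rectal value: 37.5°C is Grade 0, so a documented fever would be coded as none. A value of 39.6 to 40.0°C is Grade 2, which is not the highest category.
- Number read as an oral value and raised by 0.5: 37.5 + 0.5 = 38.0 (Grade 1), and 39.6 + 0.5 = 40.1 (Grade 3). Both are again as intended, but the offset is written for measured temperatures and does not clearly cover an imputed one.

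**Step 5. The increment table.** SAP 6.1.3 gives no first row, so its start is an assumption. If it is 38.0°C and above, an inserted 37.5°C falls in no row; if it is 37.5°C and above, it falls in the first.

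**The case against.** - **The protocol is not uniform.** The enrolment criteria (4.3) and contraindications (6.5) use 37.5°C for the tympanic route without mentioning a setting, which is the SAP's grouping. This may be where the SAP wording came from. Those sections govern enrolment and vaccination; Tables 15 and 19 govern solicited fever, so the conflict stays.
- **Exposure may be nil.** The diary card asks for rectal temperature (Protocol 5.6.14) and rectal is the preferred route. Over-grading needs an ear reading, on rectal setting, with the child's maximum in one of three bands. This stands, and it limits the importance of the point.
- **The labels do no harm as worded.** The instruction is to assign a category, and 37.5°C is inherited from Protocol 10.5, where both scales exist. The >39.5°C label is used only if more than 1% of subjects lack daily values. The second sensitivity analysis avoids it, because there "both subjects who documented the presence of an event without having recorded any daily measurement and subjects without documentation will be excluded". This also stands: on its own, the label issue would be a wording remark.
- **SAP 9 is not a closed list.** It defers the changes to be reported to the review of the study report, and Protocol 10.9 puts disclosure in the final report. That softens the criticism, but the item still has to be identified for disclosure to happen.
- **The analyses are done.** SAP 1 says the Month 0 to Month 9 specifications were kept because those analyses had already been run, and the note in SAP 5.8 confirms reactogenicity was analysed up to Month 3. Rewriting the rule without checking the program could make the SAP describe something that was not run. This is a good reason to check first.

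**Conclusion.** The concern holds. Followed exactly, SAP 7.1.2 gives a grade that contradicts the protocol for tympanic readings on rectal setting in three bands, always by one level upward, and SAP 9 does not list the change. The 37.5°C and >39.5°C labels are a scale mismatch that matters only if the numbers are inserted as rectal values.

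The reach is small. Only descriptive fever tables could change, and neither confirmatory objective is touched. The documents do not say how many tympanic readings were on rectal setting, whether the case report form captures the setting, or how many fevers lacked a daily value; the number of affected children may be zero. Confidence is high about the conflict in the text. No effect on results is claimed.

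**What to change.** 1. **Check the completed reactogenicity program**: how it treated tympanic readings, where it placed fevers with no daily value, and whether the tympanic setting was captured. Re-run the fever tables, or disclose the matter in the study report under Protocol 10.9, only if at least one subject was affected.
2. **SAP 7.1.2, conversion rule**: limit the 0.5°C offset to oral, axillary and oral-setting tympanic readings, and grade rectal-setting tympanic readings as recorded. If the setting was not captured, state that tympanic readings may be over-graded.
3. **SAP 7.1.2 and 7.2, labels**: write *Grade 1 (38.0°C rectal-equivalent)* and *Grade 3 (>40.0°C rectal-equivalent)*, and say which row of the 0.5°C increment table counts the imputed subjects.
4. **SAP 9**: add one line recording these clarifications, including that the 37.5°C in Protocol 10.5 is an oral-scale value.

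The cost is two edits in 7.1.2, one in 7.2, one line in SAP 9 and one program check. No protocol amendment is needed.

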7.2. Sensitivity Analyses

- In case the number of subjects who documented the presence of a solicited event after 1 dose without having recorded any daily measurement exceeds 1%, a sensitivity analysis will be carried out to assess the impact of assigning the lowest intensity for the event. Two (2) additional analyses will be performed for solicited events collected during the 4-day (Day 0 – Day 3) follow-up period:
 - In the first sensitivity analysis, subjects who documented the presence of an event without having recorded any daily measurement will be assigned to the highest intensity category (ie >39.5°C for fever or Grade 3 for other events), while the subjects without documentation will be excluded.
 - In the second sensitivity analysis, both subjects who documented the presence of an event without having recorded any daily measurement and subjects without documentation will be excluded.

7.3. Data Presentation Description

The following decimal description will be used for the demography, immunogenicity, and safety/reactogenicity analyses:

Display Table	Parameters	Number of decimal Digits
Demographic characteristics	Mean, median age	1
Demographic characteristics	SD (age)	1
rSBA-MenA	GMT	1
rSBA-MenC	GMT	1
rSBA-MenW-135	GMT	1
rSBA-MenY	GMT	1
hSBA-MenA	GMT	1
hSBA-MenC	GMT	1
hSBA-MenW-135	GMT	1
hSBA-MenY	GMT	1
Pneumococcal vaccine serotypes (ELISA)	GMC	2
Pneumococcal vaccine serotypes (OPA)	GMT	1
Immunogenicity	Ratio of GMT/GMC	2
All summaries	% of count, including LL & UL of CI	1
All summaries	% of difference, including LL & UL of CI	2

Abbreviations: ELISA = enzyme-linked immunosorbent assay; GMC = geometric mean concentration; GMT = geometric mean titer; LL = lower limit; OPA = opsonophagocytic activity; UL = upper limit.

7.4. Methodology for Computing CI

- All CIs computed will be 2-sided 95% CIs.
- The exact 95% CIs for a proportion within a group will be based on the method by Clopper and Pearson (Clopper and Pearson, 1934).¹
- The standardized asymptotic 95% CI for the group difference in proportions will be based on method 6 described by Newcombe (Newcombe, 1998).²
- The 95% CI for GMTs/GMCs will be obtained within each vaccine group separately. The 95% CI for the mean of log-transformed titer/concentration will be first obtained assuming that log-transformed values were normally distributed with unknown variance. The 95% CI for the GMTs/GMCs will then be obtained by exponential transformation of the 95% CI for the mean of log-transformed titer/concentration.
- The 95% CIs of the vaccine group GMC/GMT ratios will be computed using an ANCOVA model on the logarithm₁₀ transformation of the concentrations/titers. The ANCOVA model will include the prevaccination logarithm₁₀ transformation of the concentration/titers, country, number of doses of Prevenar 13 received before the study (2 or 3 doses), and vaccine group as covariates.

8. CONDUCT OF ANALYSES

8.1. Sequence of Analyses

Statistical analyses will be done stepwise:

- A first analysis will include the data collected up to Month 1 for the ACWY1d and Co-ad vaccine groups and Month 3 for the ACWY2d and PCV13 vaccine groups in order to analyze the immunogenicity endpoints related to MenACWY-TT, solicited events during the 4-day (Day 0-3) period after each vaccine dose, unsolicited AE during the 31-day (Day 0-30) period after each vaccine dose, and SAEs (the safety analysis includes both MenACWY-TT and PCV13 vaccines). The analyses will be performed on data as clean as possible.
- A second analysis will include the data collected up to Month 1 for the Co-ad vaccine group and Month 3 for the PCV13 vaccine group in order to analyze the immunogenicity endpoints related to PCV13. This analysis will also include the SAEs and NOCIs reported from administration of the first study vaccine dose until Month 9. If unsolicited AE that occurred during the 31-day (Day 0-30) period are encoded after the first analysis was performed, unsolicited AE will be analyzed again in the second analysis. These analyses will be performed on data as clean as possible.
- Further analyses will be done at the end of epochs 002, 003, and 004 and these will include data on immunogenicity endpoints. In addition, the SAEs of epoch 001 and SAEs considered related to vaccination of epochs 002, 003, and 004 will be analyzed.

The analyses of epochs 002 and 003 will be done on data as clean as possible and the analyses of epoch 004 will be done on clean data.

